10.2.3 Safety Outcomes

Several specific adverse events are monitored throughout the study (see Section 8.8). However, death from any cause within 30 (\pm 7) days of randomization is evaluated statistically during and at the end of the Trial. We propose to use the 30-day mortality as the primary safety outcome because of the observed differences between the treatment groups during that period in the Part 1 of

the ALIAS Trial. Furthermore, the causes of death during that period are suspected to be more related to the study treatment compared to deaths occurring post-30 days from randomization. Clearly, the seriousness of this event requires close monitoring; therefore, we plan to conduct frequent interim analyses of this outcome (see Section 10.7.2).

10.3 Sample Size and Accrual

The total sample size for the effect size of 10% absolute difference between the ALB and control groups in the proportion of subjects with favorable outcomes [or 25% increase in relative benefit (RB)] assuming the control group's proportion of 40%, and Type I and Type II error probabilities of 0.025 (one-sided) and 0.10, respectively, is 1,100. We assume a group sequential design with 3 interim analyses for overwhelming efficacy and concurrently, for futility based on O'Brien and Fleming [1] boundaries (after about ¼, ½, and ¾ of the subjects complete the 3-month follow-up assessments).

This sample size will allow testing of the effect of interaction between the study treatment and thrombolytic treatment. We will be able to detect an interaction effect of 20% absolute difference between the thrombolysis and non-thrombolysis strata in the magnitude of the treatment effect with 80% power at two-sided alpha of 0.10, assuming that the thrombolysis to non-thrombolysis ratio is no greater than 4:1. Note that the interaction effect will be tested only upon completion of the study and not at each of the interim analyses.

The ITT principle will be applied to the analysis. With a total sample size of 1,100, if we observe no more than 5% lost-to-follow-up, we should have approximately 85% power to detect a 10% treatment effect (i.e., the total sample size is inflated by a factor of 1.11[32]).

10.4 Data Analyses

10.4.1 Analysis of Primary Efficacy Outcome

The primary analysis for the Trial is to test the hypothesis of superiority of ALB therapy over placebo in acute ischemic stroke subjects, adjusting for the effects of thrombolysis and stroke severity. The analysis model for the primary efficacy outcome is:

$$E(Y) = \alpha + \beta_1 x_1 + \beta_2 x_2 + \beta_3 x_3 + \beta_4 x_1 x_2, \quad (1)$$

where Y= primary clinical outcome (0=unfavorable, 1=favorable), β_i is the regression coefficient, x_1 = treatment assignment (0=saline, 1=ALB), x_2 = thrombolysis treatment (0=no, 1=yes), and x_3 = baseline NIHSS score. The last term on the right hand side of the equation represents the study drug by thrombolysis interaction effect.

We will first test the interaction term. If it is not statistically significant at $\alpha=0.10$ or if it is statistically significant but the interaction is quantitative (i.e., if study drug effect is in the same direction in both strata), then we will test:

$$\beta_1 = 0 \text{ vs } \beta_1 > 0,$$

using the model:

$$E(Y) = \alpha + \beta_1 X_1 + \beta_2 X_2 + \beta_3 X_3 . \quad (2)$$

Otherwise, the primary efficacy analysis will be based only on subjects who receive thrombolytic treatment using the model:

$$E(Y) = \alpha + \beta_1 X_1 + \beta_3 X_3 . \quad (3)$$

For this test, we anticipate approximately 880 subjects in the thrombolysis stratum based on the observed recruitment ratio of 4 thrombolysis subjects to every one non-thrombolysis subject who were enrolled in the Part 1 of the Trial. If this ratio holds in Part 2, we will have insufficient sample size to test the non-thrombolysis group with adequate power; however, the data will be evaluated as exploratory analysis.

The primary analysis of the main efficacy outcome (whether the interaction is significant or not) is tested using the generalized linear model with log link function. It is tested at the one-sided alpha level of 0.025. PROC GENMOD procedure of SAS[®] v9 is used to obtain the test statistics and the results [130]. In addition, relative benefit ratio of ALB compared to saline and its 95% confidence interval are calculated.

As the primary analysis, all efficacy outcome measures will be analyzed under the ITT principle. Under this principle, the evaluable sample includes all subjects who are randomized, and each subject will be analyzed according to the treatment group to which they were randomly assigned and in the stratum to which they were classified at the time of randomization.

The primary analysis does not adjust for the clinical site effect due to the large number of sites (approximately 60-80). As a secondary analysis, we assess the ALB therapy effect adjusting for the effect of clinical sites. One such analysis is conducted with a generalized linear model containing treatment (ALB or placebo), thrombolysis, and baseline NIHSS as a fixed effect, clinical site as a random effect (due to the large number of sites), and treatment-by-site interaction effect as a random effect.

Other secondary analyses of the primary outcome at the end of the study include generalized linear model analysis adjusting for a variety of covariates that are deemed clinically or prognostically important (in addition to thrombolysis treatment and baseline NIHSS score). Prior to these analyses, univariate analyses of covariates are conducted to determine their inclusion in the multivariable models. Some of the variables suspected to be associated with the outcome measures are: age at baseline, African American race, serum glucose at baseline, systolic blood pressure at baseline, ASPECTS score from baseline CT scan, history of MI, and time from symptom onset to treatment. The usual verification of variable and model assumptions (e.g., normality and homoscedasticity) and goodness of fit assessments accompany each analysis.

Subgroup analyses are also planned, assuming sufficient numbers of subjects are enrolled in the subgroups. These analyses involving covariates are tested at the two-sided alpha level of 0.01 in order to control nominally for the inflation of Type I error. The details of these secondary analyses on the primary outcome measure are provided in the Statistical Analysis Plan.

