10.4.3 Analysis of Safety Outcome

The Cox proportional hazards model is used to analyze time to death within 30 days from randomization. The analysis adjusts for the effects of thrombolysis treatment, age (continuous), and baseline NIHSS score (continuous). The sample size of 1,100 yields an anticipated maximum number of events of 170 based on the 3.5-year subject accrual time at, on average, 1 subject per day (which is the rate observed around the time of enrollment suspension of Part 1 of the Trial) under the Type I and II error probabilities of 0.01 and 0.10, respectively.

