10.7.2 Statistical Stopping Guidelines for Safety

Because of concerns about excess deaths in one group over the other in Part 1 of the ALIAS Trial, we have established one set of statistical safety stopping guidelines based on mortality within 30 days from randomization as shown in Table 10.7.2.

Table 10.7.2 Suggested approximate stopping guidelines for safety.

Approximate N at interim monitoring*	Total # death*	Maximum split in # of death between the two groups to yield LL of 99% CI on RR < 1.0		Unadjusted RR**	LL of 99% CI for the unadjusted RR
		Group A	Group B		
100	15	3	12	4.00	0.959
200	30	9	21	2.33	0.981
300	45	16	29	1.81	0.925
400	60	22	38	1.73	0.969
500	75	29	46	1.59	0.952
600	90	35	55	1.57	0.986
700	105	42	63	1.50	0.977
800	120	49	71	1.45	0.972
900	135	55	80	1.45	0.998
1000	150	62	88	1.42	0.994
1100	165	69	96	1.39	0.991

* Assumes 15% overall 30-day death rate.

** In practice, the RR will be estimated adjusting for thrombolysis treatment, age, and baseline NIHSS, and its LL of the 99% CI will be used for stopping criterion.

The above stopping guideline is based on the total number of deaths observed within 30 days. Hence, the first interim monitoring point occurs after a total of 15 deaths are observed, which should translate to when approximately 100 subjects have had the 30-day follow up, assuming a 15% overall 30-day death rate. The 3-to-12 split of the 15 deaths yields an unadjusted RR of 4.0 with the lower limit (LL) of its one-sided 99% CI at just below 1.0. The split that is more extreme (i.e., 2-to-13, 1-to-14, or 0-to-15) will yield an LL of greater than 1.0.

Subsequent interim monitoring point occurs after every additional 15 deaths (within 30 days) are observed.

Because thrombolysis treatment, age, and baseline NIHSS are strong prognostic indicators of death, in practice, we will estimate the RR adjusting for these covariates, and we would become alerted if the LL of its one-sided 99% CI begins to approach 1.0. The DSMB will evaluate this and other pertinent data to consider stopping the trial. It would be the DSMB's prerogative to consider all information made available to them in their decision to continue or stop the trial regardless of the above suggested statistical stopping guideline.

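### Baseline age is left out of the primary and interim efficacy models: a small missed gain in precision, not an error

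*Protocol*

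**What the plan says.** Section 10.4.1 sets out three models for the primary outcome. Model (1) has treatment, thrombolysis, baseline NIHSS and the treatment-by-thrombolysis interaction. Model (2) drops the interaction. Model (3), the fallback in the thrombolysis stratum, keeps treatment and NIHSS. The stated aim is a test "adjusting for the effects of thrombolysis and stroke severity", with a log link in PROC GENMOD; the distribution is not named. Section 10.7.1 bases the interim efficacy and futility decisions on the same two covariates.

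Age appears in four other places:
- **Section 10.4.3:** the Cox model for 30-day death adjusts for thrombolysis, age and NIHSS.
- **Section 10.7.2:** the safety guideline uses a relative risk adjusted for the same three, with the reason "Because thrombolysis treatment, age, and baseline NIHSS are strong prognostic indicators of death".
- **Section 10.4.1, secondary analyses:** "Some of the variables suspected to be associated with the outcome measures are: age at baseline", followed by six more variables. Univariate analyses decide which of them enter the multivariable models. The synopsis also names age for secondary adjusted analyses.
- **Section 2.2.2:** the adjusted Phase I comparisons of the same composite outcome included age.

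Section 10.4.1 explains why site is not in the primary model (too many sites). It says nothing about why age is not.

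**The concern.** The safety analysis adjusts for three baseline predictors, and the efficacy analysis for only two of them. Section 10.6 scores death as unfavorable, so a strong predictor of death is likely to predict the primary outcome to some degree. Randomization is balanced by site (section 4.3.3) and stratified by thrombolysis (section 3), so nothing in the design controls age balance across an eligible range of 18 to 83 years.

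Adjusting for a prognostic baseline covariate normally narrows the interval for the treatment effect and takes chance imbalance in that covariate out of the estimate. Age in a secondary model, admitted after screening on the trial data, does neither for the confirmatory test or the interim decisions. At stake is some precision in the relative benefit and in the stopping statistics.

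**Working it through.** **1. Does the stated sample size depend on covariates?** Section 10.3 gives an "effect size of 10% absolute difference between the ALB and control groups", a 40% control rate, and "Type I and Type II error probabilities of 0.025 (one-sided) and 0.10, respectively, is 1,100". It has three interim looks with O'Brien-Fleming-type efficacy and futility boundaries.

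Fixed design, per arm: n = [z(0.975)·√(2·0.45·0.55) + z(0.90)·√(0.40·0.60 + 0.50·0.50)]² / 0.10² = [1.960·0.7036 + 1.282·0.7000]² / 0.01 ≈ 518, rounded up to 519, so 1,038 in total.

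Group-sequential inflation for looks at 1/4, 1/2, 3/4 and 1, by numerical integration:
- binding futility: 1.052, so 1,038 × 1.052 ≈ 1,092
- non-binding futility: 1.084, so 1,038 × 1.084 ≈ 1,125

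The stated 1,100 lies between them. Dividing the information by the protocol's factor of 1.11 for 5% loss gives 86.8% power, against a stated figure of approximately 85%. No covariate enters this arithmetic, so leaving age out does not disturb it.

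**2. How much of the primary outcome is death?** Section 10.7.2 assumes 15% 30-day mortality: 0.15 × 1,100 = 165 deaths. At 40% and 50% favorable, the unfavorable outcomes number 550 × 0.60 + 550 × 0.50 = 605. So about 165/605 = 27% of unfavorable outcomes would be 30-day deaths. The link between age and the primary outcome is plausible, but its size is not settled, since most unfavorable outcomes are in survivors of the first 30 days.

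**3. What would age add?** The protocol gives no age effect on favorable outcome, so a range is assumed. The simulation used N = 1,100, a log-link Poisson model with robust variance, 500 trials per setting, age SD about 14 years before truncation to 18-83 (the Phase I SD in section 2.2.2 was 14.9), and an NIHSS odds ratio of 1.15 per point. Thrombolysis and NIHSS were in both models.

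| Assumed OR of unfavorable outcome per 10 years | Variance reduction, log relative benefit | Equivalent extra subjects | Power from 90.0% | Power from 86.8% (after 5% loss) |
|---|---|---|---|---|
| 1.2 | about 1% | 1,100/0.990 − 1,100 ≈ 11 | 90.2% | 87.1% |
| 1.4 | 3.6% | 1,100/0.964 − 1,100 ≈ 41 | 91.0% | 87.9% |
| 1.6 | 6.5% | 1,100/0.935 − 1,100 ≈ 76 | 91.7% | 88.9% |

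At an odds ratio of 1.6 the mean standard error falls from 0.0648 to 0.0627, and the interval narrows by 1 − √0.935 ≈ 3.3%.

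A second simulation (600 trials per setting, age SD 13, log-odds of −0.015, −0.030 and −0.045 per year) gave squared ratios of mean test statistics of 1.010, 1.033 and 1.066, or about 11, 36 and 72 subjects. A third, under similar assumptions, gave 0.6% to 6% of information, with simulated power changing by −0.3 to +1.0 points.

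**4. Can the model be fitted?** In the second simulation a basic log-binomial fit failed in at most 0.5% of data sets without age and in 25% to 96% with it. In the third, convergence fell from about 100% to between 8% and 92%. A better optimizer may do better, but the direction is the same.

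**The case against.** The strongest case against is that this is a covariate preference. The primary covariates are prespecified and consistent across the synopsis and sections 10.1, 10.4.1 and 10.7.1. The Cox model concerns another outcome, singled out because of the mortality difference in Part 1, and different outcomes may have different covariates. All of that stands, and so the point is not an internal contradiction.

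Several stronger readings are tempting and not supported:
- A reader might infer that the protocol calls age strongly prognostic for the efficacy outcome. It says so only of death. For efficacy it states a suspicion, in an unranked list.
- A reader might take the Phase I adjustment as precedent. Those were non-randomized comparisons, against historical controls and between dose tiers, where adjustment guards against confounding. In a randomized trial chance age imbalance is already covered by the Type I error rate and the interval.
- A reader might tie the fall from 90% to about 85% power to the missing covariate. Section 10.3 attributes it to loss to follow-up.
- A reader might call the gain free. It is not, because the fitting method has to be fixed at the same time. In the third simulation, moving from log-binomial to robust Poisson shifted the mean test statistic more than adding age did in five of six settings (for example 3.30 to 3.42, then 3.42 to 3.43 with age). The two changes should not be credited to age together.

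What remains is that a plausible predictor, recorded for everyone, is left to screened secondary models without a stated reason.

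**Conclusion.** The point holds as a minor, optional improvement. Adding age would be expected to bring roughly 1% to 7% more information, equal to about 11 to 76 subjects, or 11 to 76 days at the one subject per day assumed in section 10.4.3. Power would rise by about 0.2 to 2 points. These figures rest wholly on assumed age effects (odds ratios of about 1.2 to 1.6 per 10 years) and an assumed age spread; at the lower end the gain is negligible. The primary analysis as written is valid, and neither the sample size nor the power statement needs to change.

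**What to change.** Before unblinding, add continuous baseline age to models (1), (2) and (3) in section 10.4.1 and to the interim model in section 10.7.1. In the same text, prespecify a log-link Poisson fit with robust variance in PROC GENMOD. This keeps the log link, the software and the relative benefit as the target, although the estimates will not be numerically identical to those of a log-binomial fit.

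If age is to stay in the secondary analyses, one sentence giving the reason, as is done for site, would close the point.

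The cost is wording in the protocol and the SAP, and the change or fixing of the fitting method. No new data are needed, since age is already recorded for eligibility.

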10.7 Data Monitoring

10.7.1 Statistical Stopping Guidelines for Overwhelming Efficacy and Futility

Three interim analyses are planned for assessment for evidence of overwhelming efficacy as well as for futility. For overwhelming efficacy, we adopt the alpha spending function approach [59], and for futility, the beta spending function approach [74]. For both overwhelming efficacy and futility, O'Brien and Fleming-type stopping guidelines are used [72]. In other words, the difference between the ALB and placebo groups must be very large early on in the study to reject the null hypothesis for overwhelming efficacy, and similarly, the difference must be very small early on in the study to "reject" the alternative hypothesis to declare futility of observing statistical differences in the treatment effect between the two groups.

The tentative stopping criteria, calculated with EAST[®] 5 software (Cytel Software, 2006), based on the 3 planned interim analyses (or a total of 4 analyses) at equal intervals during the study are provided in the SAP. These values are updated using EAST[®] 5 software. Interim analyses for consideration of stopping the study for overwhelming efficacy or for futility are based solely on the analysis of the primary outcome adjusted for thrombolysis and baseline severity. The timing and

frequency of interim analyses may be changed upon DSMB request, and the spending function approach allows for such flexibility.

Each interim analysis is conducted ignoring the interaction effect between thrombolysis and study treatment. The rationale is: (1) we expect we will have insufficient power to detect any strong qualitative interaction effect at any interim analysis; and (2) in the absence of statistical evidence of strong qualitative interaction effect, we plan to use model (2) in Section 10.4.1 as the primary efficacy analysis. However, at each interim analysis, conditional power of the test for interaction effect given the data to date and current trend will be calculated for evaluation by the DSMB.

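### The data-driven choice between a pooled and a thrombolysis-only primary test, each at one-sided 0.025, does not guarantee the stated overall error: about 0.030 with non-binding futility

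*Protocol*

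**What the plan says.** Section 10.3 sizes the trial for a 10-point absolute difference from a 40% control rate, with "Type I and Type II error probabilities of 0.025 (one-sided) and 0.10, respectively, is 1,100". It plans three interim looks, at about one quarter, one half and three quarters of the subjects, for efficacy and futility with O'Brien-Fleming-type boundaries. It treats the interaction test as two-sided at 0.10 and reserves it for the end of the study.

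Section 10.4.1 then sets a two-step primary analysis. The pooled model (2) is used in two cases: "If it is not statistically significant at $\alpha=0.10$ or if it is statistically significant but the interaction is quantitative", where quantitative means that the treatment effect has the same direction in both strata. In the remaining case, "Otherwise, the primary efficacy analysis will be based only on subjects who receive thrombolytic treatment using the model" (model (3)). For the primary test in either case, "It is tested at the one-sided alpha level of 0.025". About 880 of the 1,100 subjects are expected in the thrombolysis stratum, from the 4:1 recruitment seen in Part 1.

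Section 10.7.1 adds: "Each interim analysis is conducted ignoring the interaction effect between thrombolysis and study treatment". Interim efficacy and futility decisions therefore rest on model (2), and model (3) can enter only at the final analysis.

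**The concern.** The population for the single confirmatory test is chosen from the same outcome data that the test then uses. The switch needs opposite signs in the two strata. When the thrombolysis estimate is high by chance, the rule drops the stratum that would have pulled the pooled result down. The rule never moves to the non-thrombolysis stratum, so the selection adds wins for albumin in the thrombolysis stratum and removes few pooled ones. With full alpha in each branch, the overall error exceeds the error of either test alone.

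At stake is whether 0.025 in section 10.3 describes the trial. Section 10.4.4 rests the conclusion on effectiveness solely on the Part 2 primary outcome. The switch is not far-fetched: section 2.2.2 reads the Phase I data as suggesting an albumin-by-thrombolysis interaction.

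**Working it through.** **Inputs.** One-sided alpha 0.025, power 0.90, rates 0.40 and 0.50, N = 1,100, and interaction test two-sided 0.10 (all section 10.3); thrombolysis share f = 0.80 (880/1,100) and the switch rule (10.4.1); interims pooled only (10.7.1); 1:1 allocation (section 3).

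**Step 1: the plan's own figure.** Per arm, n = [1.960·√(2·0.45·0.55) + 1.282·√(0.40·0.60 + 0.50·0.50)]² / 0.10² ≈ 518, rounded up to 519, or 1,038 in total for a fixed design. The inflation factor for four looks with Lan-DeMets O'Brien-Fleming alpha and beta spending is 1.054 with binding futility (1,094) and 1.083 with non-binding futility (1,124). Both are within 3% of 1,100, so the stated size reproduces.

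**Step 2: the rule as statistics.** Let Z1 and Z2 be the independent test statistics for the thrombolysis and non-thrombolysis strata.
- Pooled: Zp = √f·Z1 + √(1−f)·Z2
- Interaction: Zi = √(1−f)·Z1 − √f·Z2
- Switch to Z1 if |Zi| > 1.645 and Z1, Z2 have opposite signs. Reject if the selected statistic exceeds 1.960.

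Zp and Zi are independent under the null, and Z1 = √f·Zp + √(1−f)·Zi. At f = 0.80 this is Z1 = 0.894·Zp + 0.447·Zi. With Zi just over 1.645, the second term adds 0.447 × 1.645 = 0.736. Z1 then passes 1.960 once Zp exceeds (1.960 − 0.736)/0.894 ≈ 1.37. The route to a second win is therefore easier than the pooled test.

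**Step 3: overall one-sided error, no effect in either stratum, no interims, f = 0.80.**
- The switch occurs in 8.4% of trials.
- The pooled branch contributes 0.0238 and the thrombolysis-only branch 0.0064, for a total of 0.0301 before rounding of the parts.
- By thrombolysis share: 0.0321 at 70%, 0.0311 at 75%, 0.0291 at 85%, 0.0281 at 90%.
- Simulating binomial outcomes with log relative-risk tests (440 and 110 per arm): 0.0295 with rate 0.40 in both strata, and 0.0286 with rates 0.42 and 0.32. The pooled test alone gives 0.0244 and 0.0246.

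**Step 4: with the interims.** Assumed efficacy bounds (Lan-DeMets O'Brien-Fleming): 4.333, 2.963, 2.359, final 2.014. Assumed futility bounds (O'Brien-Fleming-type beta spending at 0.10): z = −1.42, 0.31, 1.27. The protocol places the actual values in the SAP.

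| Final z, both branches | Futility non-binding | Futility always obeyed |
|---|---|---|
| 2.014 | 0.0295 | 0.0251 |
| 1.96 | 0.0326 | 0.0272 |
| 2.11 | 0.0248 | 0.0217 |

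Without the switch, the non-binding design at 2.014 gives 0.025. If the thrombolysis-only branch uses 1.96 and the pooled branch 2.014, the non-binding error is 0.0302. With futility obeyed, about 0.55% of null trials reach the final look and switch, against 8.4% when no trial stops.

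**Step 5: power for a uniform 10-point effect.** Moving the final value from 2.014 to 2.11 takes power from 91.7% to about 90.3% ignoring futility, and from 89.9% to 88.8% if futility is followed.

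**The case against.** The strongest reply is that the trial has a futility rule. The switch happens only at the final look, and under the null most trials stop before it. If every futility stop is obeyed, the error is 0.025 to 0.027 and the inflation is small or absent. This stands, and it rules out saying without condition that the error is 0.030. It does not remove the point. Section 10.7.1 presents the boundaries as guidelines and as tentative, and lets the DSMB change the timing of looks. For such rules the usual convention is to take no credit for futility when claiming error control. Any margin that full compliance gave would also be accidental.

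A reader might infer that a thrombolysis-only claim carries three times the nominal error. In null trials that switch, the rejection rate is about 7.5% (0.0064 out of 0.084). That is an error rate conditional on selection, which the protocol does not undertake to control, and it assumes no futility stops. The switched branch adds 0.0064 to the overall error.

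A reader might also take 0.0326 as the true rate, because section 10.4.1 names 0.025 for the final test. Pooled-only testing at 1.96 after the interims already gives 0.0277, so part of that excess is unrelated to the switch. Section 10.7.1 also adopts alpha spending, which makes that reading strained.

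Finally, the switch is pre-specified, confined to qualitative interaction, and can lead only to one named stratum. Section 10.7.1 gives reasons for ignoring the interaction at the interims. This justifies keeping the switch, but not giving each branch the full 0.025.

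**Conclusion.** The point holds as a should-fix. The protocol itself fixes full alpha for both branches, so this is not a detail left to the SAP. At 4:1 and under no effect in either stratum, the overall one-sided error is about 0.030 with non-binding futility and about 0.025 to 0.027 with futility always obeyed. The excess at 4:1 is thus at most about 0.5 percentage points, roughly 20% relative, and somewhat more if the thrombolysis share falls (0.032 at 70%). The documents do not support calling the trial's error control broken or the switch inadmissible. They support saying that the stated 0.025 is not guaranteed.

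The figures rest on three assumptions: Lan-DeMets O'Brien-Fleming-type bounds for efficacy and futility, the 4:1 ratio, and the two-sided reading of the 0.10 interaction level, which section 10.3 states and 10.4.1 does not repeat.

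**What to change.** Keep the pre-specified switch, but use one final critical value for both branches. Calibrate it by simulation, with the actual boundaries and the observed stratum ratio, so that the overall one-sided error is at most 0.025 with non-binding futility. Under the bounds assumed here and at 4:1, this is about z = 2.11. State the value, or the rule for computing it, in section 10.4.1, and refer to it in 10.7.1 so that the thrombolysis-only branch has a place in the error accounting. Repeat there that the interaction test is two-sided.

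The cost is protocol and SAP wording, a short simulation, and about 1 to 1.5 points of power for a uniform 10-point effect. If futility is followed, power falls to 88.8%, so the power stated in section 10.3 should be updated.

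A pooled-first fixed sequence, with model (3) tested only after pooled success, would also control the error without calibration. It gives up a stand-alone thrombolysis-only win, so it is an optional design trade-off and is not needed to resolve the point.
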